**Figure 1. Study Schematic**

## 2.3 Treatment Assignment and Blinding

Subjects will be randomized to the following treatment sequences in a 1:1 ratio:

	First Qualifying Prodrome Event	Second Qualifying Prodrome Event
Treatment Sequence A	placebo	ubrogепant 100 mg
Treatment Sequence B	ubrogепant 100 mg	placebo

Participants randomized to Treatment Sequence A will receive placebo to treat their first qualifying prodrome event and ubrogепant 100 mg to treat their second qualifying prodrome event. For those randomized to Treatment Sequence B, they will receive the reverse: ubrogепant 100 mg to treat their first qualifying prodrome event and placebo to treat their second qualifying prodrome event.

Each blister card containing study intervention will be labeled with medication kit numbers. An automated Interactive Web-Response System (IWRS) will provide the site with the specific medication kit number(s) for each randomized participant at the time of randomization (Visit 2) and at Visit 3. Sites will dispense study intervention according to the IWRS instructions at these 2 visits. Sites will receive the IWRS confirmation notifications for each transaction. All notifications are to be maintained with the study source documents.

All study interventions will be provided in identical blister cards to maintain masking of the study. Tablets of ubrogепant 50 mg and placebo will be identical in appearance.

## 2.4 Sample Size Determination

The primary efficacy parameter is the absence of a headache of moderate/severe intensity within 24 hours after taking double-blind study intervention during the prodrome. The original sample size of 600 participants randomized is based on the assumption of a response rate of 64% for the placebo group and 80% for the ubrogепant 100 mg group, 240 participants in each study intervention will provide at least 95% power to detect the above intervention difference at the two-sided 5% significance level. The nQuery

Advisor 7.0 was used for the power calculation. Assuming 20% of randomized participants will not experience a qualified prodrome event during the double-blind treatment period, 300 participants will be randomized to each treatment sequence.

A blinded sample size re-estimation has been performed as planned. Given that only 7% of participants, rather than the 20% originally assumed, had no determinable primary endpoint as observed based on the data cut of July 05, 2021, it was re-estimated that approximately 516 participants will need to be randomized to maintain the effective sample size of 480 participants.

The actual power will be higher with the crossover design as some participants will contribute 2 qualifying prodrome events during the double-blind treatment period.

### **3.0 Endpoints**

#### **3.1 Primary Endpoint**

The primary efficacy endpoint is the absence of a headache of moderate or severe (moderate/severe) intensity within 24 hours after taking double-blind study intervention during the prodrome.

#### **3.2 Secondary Endpoints**

Three secondary endpoints evaluate the efficacy of ubrogepant 100 mg to prevent and attenuate the headache phase, and to assess the ability to function normally within 24 hours after taking double-blind study intervention during the prodrome:

- Absence of a headache of moderate/severe intensity within 48 hours after taking double-blind study intervention during the prodrome.
- Ability to function normally within 24 hours after taking double-blind study intervention during the prodrome.
- Absence of a headache of any intensity within 24 hours after taking double-blind study intervention during the prodrome.

### 3.3 Other Efficacy Endpoints

Additional efficacy endpoints along with their respective clinical objectives are listed below in bullets in respect of the purposes.

To evaluate the effect of a single dose of ubrogепant (100 mg) versus placebo, administered during the prodrome, on attenuation of the headache phase:

- Absence of headache of any intensity by timepoint (1, 2, 3, 4, 6, 8, 48 hours postdose)
- Absence of moderate/severe headache by timepoint (1, 2, 3, 4, 6, 8 hours postdose)
- Absence of severe headache by timepoint (1, 2, 3, 4, 6, 8, 24, 48 hours postdose)
- Time to development of headache of any intensity within 48 hours after taking double-blind study intervention during the prodrome (Kaplan-Meier analysis)
- Time to development of headache of moderate/severe intensity within 48 hours after taking double-blind study intervention during the prodrome (Kaplan-Meier analysis)
- Time to development of headache of severe intensity within 48 hours after taking double-blind study intervention during the prodrome (Kaplan-Meier analysis)

To evaluate the effect of a single dose of ubrogепant (100 mg) versus placebo, administered during the prodrome, on prodrome symptoms, nonheadache migraine symptoms (photophobia, phonophobia, nausea, and dizziness), and aura:

- For each of the 5 most common individual prodrome symptoms:
  - Absence of any intensity at each timepoint
  - Absence of moderate/severe intensity at each timepoint
  - Absence of severe intensity at each timepoint
  - Time to absence of any intensity
- After a headache of any intensity is reported:

- Absence of nonheadache migraine symptoms (photophobia, phonophobia, nausea, dizziness) at each timepoint
- Absence of nonheadache migraine symptoms (photophobia, phonophobia, nausea, dizziness) of moderate/severe intensity at each timepoint
- Absence of nonheadache migraine symptoms (photophobia, phonophobia, nausea, dizziness) of severe at each timepoint
- Absence of aura at each timepoint

To evaluate the effect of a single dose of ubrogепant (100 mg) versus placebo on use of rescue medication:

- Rescue medication use within 24 and 48 hours after taking double-blind study intervention
- Time to rescue medication use within 48 hours after taking double-blind study intervention (Kaplan-Meier analysis)

### **3.4 Safety Endpoints**

The safety parameters include AEs, clinical laboratory, ECG, vital signs, physical examinations, and C-SSRS. For clinical laboratory, vital signs, and ECG parameters, the last non-missing safety assessment before the first dose of double-blind study intervention will be used as the baseline for all analyses of that safety parameter.

### **3.5 Additional HEOR Endpoint(s)**

To evaluate the effect of a single dose of ubrogепant (100 mg) versus placebo, administered during the prodrome, on satisfaction and Activity Limitation:

- Satisfaction with study medication at 8 and 24 hours after taking double-blind study intervention during the prodrome
- Activity Limitation within 24 hours after taking double-blind study intervention during the prodrome.

## 4.0 Analysis Populations

The analysis populations will consist of participants as defined below:

**Table 2. Analysis Populations**

Population	Definition	Study Intervention
Intent-to-treat (ITT)	All randomized participants. Participants will be summarized according to the randomized study sequence intervention.	Randomized
Safety	All treated participants who take $\geq 1$ administration of study intervention. Participants will be summarized according to the study intervention they actually received.	Actual received
Modified Intent-to-treat (mITT)	All randomized participants with $\geq 1$ assessment of headache occurrence within 24 hours after taking double-blind study intervention for at least 1 qualifying prodrome event during the double-blind treatment period. Participants will be summarized according to the randomized study intervention.	Randomized

For efficacy analyses, data will be analyzed according to participants' randomization assignments, regardless of actual study intervention received.

For safety data analyses, data will be analyzed according to participants' actual study intervention received (rather than as randomized).

## 5.0 Subject Disposition

Participant disposition encompasses the distribution of participants who enter, complete, and discontinue in the screening and double-blind treatment periods. Specifically, the number and percentage of participants with each disposition status in the screened, ITT, safety, and mITT populations will be summarized by treatment sequence and treatment. For participants who discontinue, the number and percentage of participants discontinued with one qualifying prodrome event, and with no qualifying prodrome event will be summarized.

## **6.0 Study Drug Duration and Compliance**

Study treatment compliance will be provided for the safety population. A summary of treatment compliance to the dose of each study medication in terms of the number and percentage of participants who took two tablets or only one tablet will be provided by study intervention.

## **7.0 Demographics, Baseline Characteristics, Medical History, and Prior/Concomitant Medications**

### **7.1 Demographics and Baseline Characteristics**

Demographic parameters (age; age group [ $<20$ , 20 to 29, 30 to 39, 40 to 49, 50 to 59, 60 to 69,  $\geq 70$ ]; sex; race; ethnicity, weight; height; and body mass index, calculated as  $\text{weight [kg]} / (\text{height [m]}^2)$ ) will be summarized descriptively by treatment sequence and treatment for the safety population. In general, unless otherwise specified, continuous variables will be summarized by number of participants with observed values (n), mean, standard deviation (SD), median, 1st and 3rd quartiles (Q1, Q3), minimum (min), and maximum (max). Categorical variables will be summarized by number of participants with observed values or events (n), frequency count (N1), and percentage of participants with observed values or events.

### **7.2 Medical and Migraine History**

Medical history data will be coded using the Medical Dictionary for Regulatory Activities (MedDRA). The number and percentage of participants with abnormalities in medical and surgical history in each system organ class (SOC) and preferred term (PT) will be summarized by treatment sequence and treatment for the safety population.

Migraine history (diagnosis, duration of migraines, whether migraine prescription medications have been taken currently or in the past, acute migraine medications that were taken, and whether prescription preventive migraine medications have been taken currently or in the past), prodrome symptom history (percentage of migraine headaches that are preceded by prodrome symptoms, symptoms, and time until headache onset for

each symptom), cardiovascular disease and risk (presence of cardiovascular disease and risk factors), historical triptan response (whether triptan was taken; reason if not taken; If taken, whether triptan relieve pain completely within 2 hours more than half the time and whether triptan was stopped in the past and the reasons), failed prevention therapy (medication currently taken and medication used in the past for migraine prophylaxis, whether the medication met failure definition and the primary reason, and whether the medication is 'not suitable' and the primary reason), and allodynia (ASC-12) questionnaire (allodynia score for each of the 12 questions and the severity based on ASC total score range: none [0-2], mild [3-5], moderate [6-8], severe [9 or more], and total score) will be summarized by treatment sequence and treatment in the safety population.

### **7.3 Prior and Concomitant Medications**

The medication data will be coded using the World Health Organization (WHO) Drug Dictionary Enhanced Version. Prior medication is defined as any medication taken prior to the start of first study intervention regardless of stop date of the medication.

Concomitant medication by treatment is defined as any medication taken after the start of study intervention (and before the next intervention if any) regardless of the start date of the medication. Prior and concomitant medications will be summarized using the Anatomical Therapeutic Chemical code (4th level, or most specific level available if 4th level is unavailable).

Prior and concomitant medications will be summarized by treatment for the safety population. The number and percentage of participants reporting prior or concomitant medications will be summarized further by ATC class and code, and preferred drug name. If more than one medication is coded to the same preferred drug name for the same participant, the participant will be counted only once for that preferred drug name.

## **8.0 Efficacy Analyses**

### **8.1 General Considerations**

Efficacy measurement assessments are based on information recorded by the participant in an eDiary.

- Absence/Presence of and Rating of Intensity of Prodrome Symptom(s)

After experiencing each qualifying prodrome event, the absence or presence of each identified prodrome symptom(s) will be followed (up to 48 hours) and the intensity subjectively rated (mild, moderate, or severe) for those that are present.

- Absence/Presence of Headache and Rating of Headache Intensity

After the prodrome symptoms have started, the participant will be alerted to record the presence of a headache when it occurs or record the absence/presence at various timepoints (up to 48 hours) following the dose of double-blind study intervention (during the double-blind treatment period). If a headache is reported as present, the intensity will be subjectively rated (mild, moderate, or severe).

- Absence/Presence of and Rating of Intensity of Nonheadache Symptoms

The participant will record whether nonheadache symptoms (photophobia, phonophobia, nausea, and/or dizziness) were absent or present as well as the intensity (mild, moderate, or severe) of the present nonheadache symptom (up to 48 hours).

- Absence/Presence of Aura

The participant will record whether aura was present or absent (up to 48 hours).

- Health outcome assessments

The functional disability scale (FDS), a single item used to measure the participant's level of functional disability, will be used to rate the performance of daily activities using 4 response options ranging from 0 (no disability, able to function normally) to 3 (severely impaired, cannot do all or most things, bed rest may be necessary). The measure will be taken at predose (baseline) and 1, 2, 3, 4, 6, 8, 24, and 48 hours after double-blind study intervention for treating the first and second qualifying prodrome events.

Overall satisfaction with study medication for migraine will be assessed using a single-item 7-point rating scale ranging from extremely satisfied (0) to extremely dissatisfied (6). The question will be answered by the participants in their eDiary at 8 hours and 24 hours after taking double-blind study intervention for treating the first and second qualifying prodrome events.

A single-item measure assessing activity limitation based on a 24-hour recall will be administered as an additional health outcome measure. The measure will be used to evaluate activity limitation with a 5-level response ranging from "Not at all limited – I could do everything" to "Extremely limited." The measure will be administered at 24 hours after taking double-blind study intervention.

The following are general considerations for efficacy analyses:

- Efficacy analyses will be performed based on mITT population.
- Continuous variables will be summarized by number of participants with observed values (n), mean, standard deviation (SD), median, 1st and 3rd quartiles (Q1, Q3), minimum (min), and maximum (max).
- Categorical variables will be summarized by number of participants with observed values or events and percentages based on the specified population.
- The efficacy analyses will be performed using a GLMM in the observed binary response variable unless an imputation method is specified.
- The least squares mean (LSMEAN) estimates of the treatment effects for the primary and secondary endpoints alongside its 95% CI will be presented.

- All statistical hypothesis tests will be performed at the 2-sided 5% significance level.
- Efficacy analyses will be presented by treatment or study intervention randomized (placebo or ubrogepant 100 mg).

## 8.2 Handling of Missing Data

Participants are expected to treat two qualifying prodrome events in the double-blinded treatment period. For each prodrome event, endpoints are derived based on all assessments recorded in the prodrome event. Missing data at prodrome event level and within prodrome event level (indeterminable endpoints within prodrome event level) will be handled using the following methods for the sensitivity analyses: non-responder imputation (NRI) for indeterminable endpoints, imputation under missing at random (MAR) for indeterminable endpoints, imputation under missing not at random (MNAR) for missing prodrome events and under MAR for indeterminable endpoints, and Period 1 data only.

**Table 3. Missing data handling at prodrome level and within prodrome level**

Analyses	Missing prodrome event	Indeterminable endpoints within prodrome event level
Primary analysis	Ignore and no imputation	Set as missing and no imputation
Sensitivity analysis 1: NRI for indeterminable endpoints	Ignore and no imputation	Set as non-responder
Sensitivity analysis 2: imputation under MAR for indeterminable endpoints	Ignore and no imputation	Sequential multiple imputation
Sensitivity analysis 3: imputation under MNAR for missing prodrome events and under MAR for indeterminable endpoints	MNAR	Sequential multiple imputation
Sensitivity analysis 4: Period 1 only	Ignore and no imputation	Set as missing and no imputation

For sensitivity analysis 2, indeterminable endpoints will be imputed using multiple imputation under MAR. The determinations of the efficacy endpoints are described in the corresponding endpoints sections. Specifically for the primary endpoint, for a participant who has not experienced headache of moderate/severe intensity by time  $t_j$  after study intervention and has missing headache severity assessment at the next timepoint  $t_{j+1}$ , whether the participant will experience headache of moderate/severe intensity at  $t_{j+1}$  will be imputed based on other participants on the same treatment who have not experienced headache of moderate/severe intensity by time  $t_j$  but have observed headache severity assessment at  $t_{j+1}$ . Base will be used in the imputation logistic model. Base is a continuous variable denoting the percentage of absence of moderate/severe headache within time  $t_{j+1}$  during the screening period. So firstly, the missing headache severity assessment by time  $t_1$  will be imputed. The missing headache by the following timepoints (2, 3, 4, 6, 8, 24, and 48 hours) will be imputed step by step similarly. One hundred datasets will be imputed.

For sensitivity analysis 3, indeterminable endpoints will be imputed using multiple imputation under MAR, and endpoints in missing prodrome events will be imputed under MNAR. One hundred datasets will be imputed.

- For participants who go through the 60-day double-blind treatment period with only one qualifying prodrome event due to lack of qualifying event or having an event but with no headache assessment, the missing data for the missing qualifying prodrome event will be considered as missing at random using multiple imputation.
- For participants who discontinued the double-blind treatment period with only one qualifying prodrome event for other reasons, the missing data for the qualifying prodrome event will be imputed based on the observed data for the second qualifying prodrome event from participants who use placebo to treat the second qualifying prodrome event.

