6.3. Measures to Minimize Bias: Randomization and Blinding

Prior to initiation of study treatment, each participant who provides informed consent will be assigned a participant number that will serve as the participant identification number on all study documents.

An automated IWRS will be used to manage the randomization and assignment to study intervention. Before the study is initiated, log-in information and directions for the IWRS will be provided to each site. Study intervention will be dispensed at Visit 2 (one blister card) and Visit 3 (one blister card) as summarized in the SoA (Section 1.3).

At the time of randomization (Visit 2), eligible participants will be randomly assigned either Treatment Sequence A or B in a 1:1 ratio in this crossover study. All participants will be instructed to take 2 tablets for each dose of study intervention regardless of the treatment sequence they are assigned. As this is a crossover study, the study intervention for the first and second qualifying prodrome event will be the reverse for the two treatment sequences. Table 6-2 below outlines the study intervention administered for each treatment sequence.

Table 6-2 Study Interventions Administered for Each Treatment Sequence

Treatment Sequence	First Qualifying Prodrome Event	Second Qualifying Prodrome Event
	Single Dose (2 tablets)	Single Dose (2 tablets)
Treatment Sequence A	placebo/	ubrogepant 50 mg/
	placebo	ubrogepant 50 mg
Treatment Sequence B	ubrogepant 50 mg/	placebo/
	ubrogepant 50 mg	placebo

The sponsor's biostatistics (randomization programmer) will prepare the randomization codes.

Each blister card containing study intervention will be labeled with medication kit numbers. IWRS will provide the site with the specific medication kit number(s) for each randomized participant at the time of randomization (Visit 2) and at Visit 3. Sites will dispense study intervention according to the IWRS instructions at these 2 visits. Sites will receive the IWRS confirmation notifications for each transaction. All notifications are to be maintained with the study source documents.

All study interventions will be provided in identical blister cards to maintain masking of the study. Tablets of ubrogepant 50 mg and placebo will be identical in appearance.

Once a randomization number has been assigned, it must not be reassigned. Withdrawn study participants will not be replaced. Returned study intervention should not be redispensed to the participants.

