9.2. Sample Size Determination

The primary efficacy parameter is the absence of a headache of moderate/severe intensity within 24 hours after taking double-blind study intervention during the prodrome. Based on the assumption of a response rate of 64% for the placebo group and 80% for the ubrogepant 100 mg group, 240 participants in each study intervention will provide at least 95% power to detect the

above intervention difference at the 2-sided 5% significance level. The nQuery Advisor 7.0 was used for the power calculation.

A blinded sample size re-estimation has been performed as planned. Given that 7% of participants had no determinable primary endpoint as observed based on the data cut of July 5, 2021, approximately 516 participants will be randomized to maintain the effect sample size of 480 participants.

The actual power will be higher with the crossover design as some participants will contribute 2 qualifying prodrome events during the double-blind treatment period.

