**Table 4. Summary of the Primary Estimand Attributes of the Primary Efficacy Endpoint**

Estimand Label	Attributes of the Estimand				
	Treatment	Endpoint	Population	Handling of Intercurrent Events	Statistical Summary
Primary	Treatment A: placebo Treatment B: ubrogepant 100 mg Placebo or ubrogepant 100 mg are assigned based on the 2x2 crossover to treat two qualifying prodrome events (Sequence A: placebo/ubrogepant 100mg, Sequence B: ubrogepant 100mg/placebo).	Absence of a headache of moderate/severe intensity within 24 hours after taking double-blind study intervention during the prodrome	mITT population (randomized participants with $\geq 1$ assessment of headache occurrence within 24 hours after taking double-blind study intervention for at least 1 qualifying prodrome event during the double-blind treatment period)	IE 1 at prodrome event level: data after the discontinuation will be handled by hypothetical strategy and assumed MAR. IE2 within prodrome event level: participants who took rescue medication within 24 hours will be counted as non-responder for the prodrome. IE3 within prodrome event level: indeterminable primary endpoint due to missing data during the prodrome will be set as missing and assumed MAR.	Treatment comparison (odds ratio) of percentages of absence of moderate/severe headache within 24 hours after taking ubrogepant 100mg vs placebo during the prodrome

The status of the primary endpoint will be determined as shown in [Figure 2](#).

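### The imputation of indeterminable endpoints in sensitivity analyses 2 and 3 leaves out current mild headache, which the eDiary records and which plausibly predicts progression

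*SAP*

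**What the plan says.** Table 3 in SAP Section 8.2 assigns sequential multiple imputation to indeterminable endpoints in sensitivity analyses 2 and 3. The text below the table spells it out for the primary endpoint. If someone free of moderate/severe headache to t_j has no severity entry at t_{j+1}, the outcome there "will be imputed based on other participants on the same treatment who have not experienced headache of moderate/severe intensity by time" t_j and who were observed at t_{j+1}. Then "Base will be used in the imputation logistic model". Base is the screening-period percentage free of moderate/severe headache by t_{j+1}. No other covariate is named. The steps run from 1 to 48 hours, with 100 imputed datasets. Protocol Section 9.4.1.2 gives the same scheme without Base, and SAP Section 8.4.1 reuses it for the first and third secondary endpoints.

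Related text:

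- SAP Section 8.1 and Protocol Section 8.1 have intensity (mild, moderate, severe) rated whenever a headache is present.
- Protocol Section 9.4.1.2 calls an event indeterminable when no moderate/severe headache was reported and the 24-hour recall is missing.
- SAP Table 4 states that "participants who took rescue medication within 24 hours will be counted as non-responder for the prodrome".
- The primary model in SAP Section 8.3.3 has period, treatment and an unstructured covariance between a participant's two events.
- In sensitivity analysis 3, an event that is missing altogether is handled separately. After discontinuation for other reasons it is drawn from Period 2 placebo data. After lack of a qualifying event it is imputed under MAR, with no model given.

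**The concern.** Given treatment and Base, a participant whose last entry was a mild headache gets the same imputed risk at the next timepoint as one whose last entry was no headache. Mild headache is the natural step before a moderate one. Mild headaches should also mostly stay in the at-risk set, because Protocol Section 6.5.3 does not permit rescue for them in the first 24 hours. With the recall missing, the deciding step is often 8 to 24 hours, where the last recorded state should carry most information.

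MAR given the stated covariates fails if mild headache predicts both stopping the diary and later moderate/severe headache. At stake is how much reassurance analyses 2 and 3 give for the primary endpoint and the 48-hour moderate/severe endpoint, the first in the gatekeeping order after the primary. The any-intensity endpoint is not affected in this way, since a mild headache already decides it.

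**Working it through.** **1. The plan's own figures.** Inputs are "a response rate of 64% for the placebo group and 80% for the ubrogepant 100 mg group" and "240 participants in each study intervention will provide at least 95% power" (Protocol Section 9.2), two-sided 5%. A normal-approximation test of two proportions with 240 per group gives 97.6% power, which meets the claim. With "7% of participants had no determinable primary endpoint", 480/0.93 = 516.1, matching about 516. The design odds ratio is (0.80/0.20)/(0.64/0.36) = 2.25, with log 0.81. The 7% is per participant. The per-event share that this imputation acts on is not given, so 7% and 15% of events are taken as an assumed range.

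**2. How an error in imputed risk reaches the arm rate.**

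Error in arm rate = share indeterminable × (imputed − true response among those events).

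A three-state simulation (none, mild, moderate/severe) assumed true response of 63% and 81%, 6–7% of events indeterminable, an 8-to-24-hour placebo risk of 4% after no headache and 27% after mild, and diaries stopping 4 times as often after mild headache in both arms.

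- Placebo: imputed 75.6%, true 68.6%, so (0.06 to 0.07) × 7.0 = 0.42 to 0.49 points too high.
- Ubrogepant: imputed 88.0%, true 83.6%, so (0.06 to 0.07) × 4.4 = 0.26 to 0.31 points too high.
- The errors partly cancel: the difference shifts by 0.42 − 0.26 = 0.16 to 0.49 − 0.31 = 0.18 points.
- With arm-specific stopping they do not cancel: 17.7 against a true 18.3, or 18.7 against a true 18.1, depending on the arm.

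**3. Bias in the log odds ratio.** A two-period crossover simulation (60,000 participants, calibrated to 64%/80%) assumed that mild headache raises the odds of progression 4-fold, a between-participant SD of 1 on the logit scale, and a missingness odds ratio of 5 for mild headache. Simulation noise is about 0.005. The enriched model adds mild state, period and the other event.

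| Events indeterminable and pattern | Primary | SAP imputation | Enriched |
|---|---|---|---|
| 7%, stopping depends on mild, placebo only | −0.007 | −0.026 | +0.001 |
| 7%, stopping depends on mild, ubrogepant only | +0.018 | +0.024 | 0.000 |
| 7%, missed recall depends on mild, ubrogepant only | −0.009 | +0.021 | 0.000 |
| 7%, missed recall depends on mild, placebo only | +0.026 | −0.022 | −0.004 |
| 7%, missed recall depends on mild, both arms | +0.011 | 0.000 | −0.003 |
| 7%, stopping unrelated to headache, 3 times the odds on ubrogepant | −0.027 | −0.003 | +0.008 |
| 15%, stopping depends on mild, placebo only | −0.025 | −0.058 | −0.011 |
| 15%, stopping depends on mild, ubrogepant only | +0.031 | +0.047 | −0.012 |
| 15%, stopping unrelated to headache, equal arms | +0.002 | −0.001 | −0.010 |

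Intensity alone does most of the work. In the two one-arm missed-recall rows it leaves −0.001 (ubrogepant) and −0.003 (placebo); in the two one-arm rows at 15% it leaves −0.006 and −0.016. Adding period and the other event moves the log odds ratio by at most about 0.015 more.

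**4. Why the enriched model is imperfect.** It carried the last mild status forward after the diary stopped. With random stopping at 15% it gives 65.0%/80.6% against a true 64.2%/80.3%. With only the last interval missing, where nothing has to be carried, it gives 64.2%/80.2%. So intensity should be imputed forward at each step. That version was not itself simulated.

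**5. Scale.** For 480 participants with two events each, treating events as independent, the standard error is √[1/(480×0.64×0.36) + 1/(480×0.80×0.20)] = √(0.00904 + 0.01302) = 0.149. Positive within-participant correlation lowers it, so about 0.14 is used. Then 0.026/0.14 = 0.19 and 0.058/0.14 = 0.41 standard errors. On the odds ratio, 2.25 × e^(−0.026) = 2.19 and 2.25 × e^(−0.058) = 2.12.

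**The case against.** The strongest reply is that the planned imputation often improves on the primary analysis. A reported moderate/severe headache always stays determinable, while a success needs the recall, so dropping indeterminable events discards mainly successes. With randomly missed recall at 7%, the primary gives 62.3%/79.1% against a true 64.2%/80.3%, and the SAP imputation gives 64.1%/80.3%. The table has further rows where it is closer, including one in which missingness depends on mild headache in the placebo arm only. This stands: a reader might infer that the imputation is generally worse than the analysis it checks, and that is not supported.

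Three other inferences also go too far:

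- That only treatment and Base are used. Donors must also be free of moderate/severe headache to t_j, and analysis 3 uses Period 2 placebo data for some missing events.
- That rescue is ignored. Recorded rescue within 24 hours already settles the endpoint, so such an event is not imputed. What is left is narrow: the text does not say how a donor who took rescue without reporting moderate/severe headache is coded. Figure 2 may settle this but is not shown in the copy reviewed.
- That this is the only robustness check. Table 3 also has non-responder imputation and a Period 1 analysis, and none of the sensitivity analyses enters the gatekeeping in SAP Section 12.0.

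The progression and stopping rates are also assumptions; nothing in the documents fixes them. None of this supplies a reason to leave out current intensity, which is collected and close to the outcome.

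**Conclusion.** The omission is real and its effect is small. The stated imputation model does not use current mild headache, so its MAR assumption is stronger than the collected data require. If stopping depends on mild headache differently by arm, the imputed odds ratio can be slightly more biased than the primary: up to about 0.03 in log odds ratio at 7% of events indeterminable and about 0.06 at 15%, or roughly 0.2 and 0.4 of a standard error, against a design value of 0.81. It can equally be as close or closer under other patterns. These sizes rest on the assumed progression odds, stopping odds and per-event share. The trial's conclusion is unlikely to change. The case for acting is that a robustness check should use the most informative recorded predictor when doing so costs little.

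**What to change.** In SAP Section 8.2, for the primary endpoint and the 48-hour moderate/severe endpoint:

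- Add last observed headache intensity (none or mild) to the imputation logistic model, alongside treatment and Base.
- Impute intensity forward with the sequence, so each later step uses an observed or imputed state and not one carried forward.
- State that donors who took rescue medication count as failures, in line with Table 4.
- Optionally add period and the participant's response at the other event, to match the analysis model. They contribute little.

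The cost is SAP wording and modest programming. The downside is a slightly larger model, with possible sparse cells at early timepoints.
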